2.5.4. Multiplicity

The study is considered as a success only if all the eight (8) co-primary immunogenicity endpoints meet the noninferiority criterion. Each of the co-primary immunogenicity endpoints will be tested at 2-sided alpha of 0.05 level.

2.5.5. Safety Analysis

The following safety analyses apply to Part A, Part B, and Part C, unless otherwise specified:

All safety analyses will be based on the Safety Set, except summaries of solicited ARs, which will be based on the Solicited Safety Set. All safety analyses will be provided by vaccination group corresponding to the study intervention that was actually received, unless otherwise specified.

Safety and reactogenicity will be assessed by clinical review of all relevant parameters, including solicited ARs (local and systemic ARs), unsolicited AEs (including any clinical safety laboratory abnormalities), treatment-related AEs, severe AEs, SAEs, MAAEs, AEs leading to discontinuation from study participation, AESIs, vital sign measurements, and physical examination findings.

When summarizing the number and percentage of participants with an event, participants with multiple occurrences of the same AE/AR or a continuing AE/AR will be counted once. Participants will be presented according to the highest severity/toxicity in the summaries by severity/toxicity, if participants reported multiple events under the same SOC and/or PT. SOC will be displayed in an internationally agreed order. PT will be displayed in descending order of frequency of mRNA-1010 vaccination group within each SOC.

2.5.5.1. Analysis of Solicited Adverse Reactions

Solicited ARs are a subset of AEs consisting of selected signs and symptoms that participants are asked to record/report. In this study, the solicited ARs are reactogenicity events. The term "reactogenicity" refers to the occurrence of transient adverse effects associated with study intervention dosing. The eDiary will solicit daily participant reporting of ARs using a structured checklist. Participants will record such occurrences in the eDiary on the day of study intervention dosing and 6 subsequent days.

Any solicited AR that meets any of the following criteria must be entered into the participant's source document and must also be recorded by the clinic staff in EDC, where reactogenicity is collected:

- Solicited local or systemic AR that results in a visit to a healthcare practitioner (MAAE).
- Solicited local or systemic AR persisting beyond 7 days post study intervention dosing.
- Solicited local or systemic AR that leads to participant discontinuation from study participation.
- Solicited local or systemic AR that otherwise meets the definition of an SAE.

The Toxicity Grading Scale for Healthy Adult and Adolescent Volunteers Enrolled in Preventive Vaccine Clinical Trials will be used to categorize local and systemic solicited ARs.

The following local ARs will be solicited by the eDiary: injection site pain, injection site erythema (redness), injection site swelling/induration (hardness), and axillary (underarm) swelling or tenderness ipsilateral to the side of injection.

The following systemic ARs will be solicited by the eDiary: headache, fatigue, myalgia (muscle aches all over body), arthralgia (joint aches in several joints), nausea/vomiting, chills, and fever (oral).

Analyses of solicited ARs will be provided by vaccination group based on the Solicited Safety Set, unless otherwise specified. All solicited ARs (overall, local, and systemic) reported during the 7-day follow-up period after injection will be summarized. The number and percentage along with its 2-sided 95% exact CI (using the Clopper-Pearson method) of participants with any solicited local AR, solicited systemic AR, and solicited AR during the 7-day follow-up period

mRNA-1010-P303

Statistical Analysis Plan, Version 2.0 Date Issued: 03APR2024

after the injection will be provided. The same analysis will be conducted for subgroups defined by age group 1, age group 2, race, and sex, see Table 5.

The number and percentage of participants who reported each individual solicited local AR (has a toxicity grade of Grade 1 or greater) and solicited systemic AR (has a toxicity grade of Grade 1 or greater) during the 7-day follow-up period after injection will be provided by toxicity grade. The same analysis will be conducted for subgroups defined by age group1, age group 2, race, and sex.

The number and percentage of participants with onset of individual solicited AR will be summarized by study day relative to the injection (Day 1 through Day 7). The onset of individual solicited AR is defined as the time point after injection at which the respective solicited AR first occurred. Descriptive statistics will be provided for the duration of solicited ARs (overall, local, and systemic) and each individual solicited AR by vaccination group. The duration of local or systemic solicited ARs, along with the specific individual solicited ARs, will be calculated as: reaction end date – reaction start date +1, no matter it is intermittent or continued or if the solicited AR continues beyond 7 days. All solicited ARs that continue beyond 7 days post-injection will be summarized. All delayed ARs with onset day after 7 days post-injection may also be summarized.

Solicited local and systemic ARs will be provided in a listing. All solicited ARs that continue beyond 7 days post-injection will be listed as well.

2.5.5.2. Unsolicited Adverse Events

An unsolicited AE is an AE that was not solicited using a participant diary and that is communicated by a participant who has signed the informed consent. A TEAE is defined as any event that does not present before exposure to IP or any event already present that worsens in intensity or frequency after exposure.

An MAAE is an AE that leads to an unscheduled or scheduled visit to a healthcare practitioner. AESIs is an AE (serious or nonserious) of scientific and medical concern specific to the Sponsor's product or program, for which ongoing monitoring and immediate notification by the

Statistical Analysis Plan, Version 2.0 Date Issued: 03APR2024

investigator to the Sponsor are required. AESI for this study are pre-defined in the protocol Section 5.4 including thrombocytopenia, new onset of or worsening of the neurologic diseases, anaphylaxis, and myocarditis/pericarditis.

Detection of all AEs will be through 28 days after study intervention dosing (i.e., the day of study intervention dosing and 27 subsequent days). Detecting MAAEs, AESI, SAEs, and AEs leading to discontinuation from study participation will continue through Day 181 (Month 6)/EoS.

All summary tables (except for the overall summary of AEs) for unsolicited AEs will be presented by SOC and PT or by PT only for TEAEs with counts of participants included. Summary tables for unsolicited AEs will be based on treatment-emergent AEs, unless otherwise specified. Listings for unsolicited AEs will be based on treatment-emergent AEs and AEs that occurred before the IP administration and will be flagged.

Unsolicited TEAEs will be summarized up to 28 days after vaccine injection. Treatmentemergent MAAEs, AESIs, SAEs, and AEs leading to discontinuation from study participation will be summarized throughout the study (up to Day 181/EoS).

In addition, number of participants with occurrences of selected TEAEs of clinical interests identified by SMQ will be summarized. SMQ will be summarized by PT, if applicable. Detailed description of SMQ is presented in The following applies to Part A, Part B, and Part C:

Table 20. Additional SMQs may be summarized, as necessary.

2.5.5.2.1. Overview of Unsolicited AEs

An overall summary of unsolicited TEAEs up to 28 days after vaccine injection including the number and percentage of participants who experienced the following will be presented:

- Any unsolicited TEAEs
- Any unsolicited treatment-related TEAEs
- Any serious TEAEs
- Any treatment-related serious TEAEs
- Any unsolicited severe TEAEs
- Any unsolicited treatment-related severe TEAEs

- Any unsolicited medically attended TEAEs
- Any unsolicited treatment-related medically attended TEAEs
- Any unsolicited treatment-emergent AESI
- Any unsolicited TEAEs leading to discontinuation from participation in the study

Listings containing individual participant AE data for unsolicited AEs, unsolicited AEs leading to discontinuation from participation in the study, SAEs, AESI, MAAEs will be provided separately.

2.5.5.2.2. Unsolicited AEs by SOC and PT

The following summary tables of TEAEs up to 28 days after vaccine injection will be provided by SOC and PT using frequency counts and percentages (i.e., number and percentage of participants with an event) and number of events:

- Any unsolicited TEAEs
- Any unsolicited treatment-related TEAEs
- Any serious TEAEs
- Any treatment-related serious TEAEs
- Any unsolicited severe TEAEs
- Any unsolicited treatment-related severe TEAEs
- Any unsolicited medically attended TEAEs
- Any unsolicited treatment-related medically attended TEAEs
- Any unsolicited treatment-emergent AESI
- Any unsolicited TEAEs leading to discontinuation from participation in the study

Unsolicited TEAEs and unsolicited treatment-related TEAEs will be summarized by SOC and PT for TEAEs with occurrence in \geq 1% of participants in any vaccination group based on PT, and also presented by SOC, PT, and severity using frequency counts and percentages.

Summary tables for all unsolicited SAEs, AESIs, MAAEs, AE leading to discontinuation from the study, and TEAE leading to death through Day 181/EoS will also be provided by SOC and PT as applicable.

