2.7.1.1. Participant Discontinuation/Withdrawal from the Study

A participant may withdraw from the study at any time at the participant's own request for any reason (or without providing any reason).

A participant may be withdrawn at any time at the discretion of the Investigator for safety, behavioral, or compliance reasons.

At the time of discontinuing from the study, if possible, the Investigator will request that the participant complete all study procedures pending at the time of withdrawal, as shown in the SoA (Table 1).

The participant will be permanently discontinued from the study participation at that time.

A participant who withdraws from the study will not be replaced.

If the participant withdraws consent for disclosure of future information, the Sponsor may retain and continue to use any data collected before such a withdrawal of consent.

If a participant withdraws from the study, the participant may request destruction of any samples taken and not tested, and the Investigator must document this in the site study records.

The Sponsor will continue to retain and use all research results that have already been collected for the study evaluation. All biological samples that have already been collected may be retained and analyzed at a later date (or as permitted by local regulations).

From an analysis perspective, a "withdrawal" from the study refers to a situation wherein a participant does not return for the final visit foreseen in the protocol. All data collected until the date of withdrawal or last contact of the participant will be used for the analysis. A participant is considered a "withdrawal" from the study when no study procedure has occurred, no follow up has been performed, and no further information has been collected for that participant from the date of withdrawal or last contact.

Information relative to the withdrawal will be documented in the eCRF. The Investigator will document whether the decision to withdraw a participant from the study was made by a participant, or by the Investigator, as well as which of the following possible reasons was responsible for withdrawal:

- Adverse event
- Death
- LTFU
- Noncompliance with study procedures
- Physician decision
- Pregnancy
- Protocol deviation
- Study terminated by Sponsor
- Withdrawal by participant
- Withdrawal due to solicited AR/reactogenicity
- Other

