2.8.3.9. Solicited Adverse Reactions

Solicited ARs are a subset of AEs consisting of selected signs and symptoms that participants are asked to record/report. In this study, the solicited ARs are reactogenicity events. The term "reactogenicity" refers to the occurrence of transient adverse effects associated with study intervention dosing. The eDiary will solicit daily participant reporting of ARs using a structured

checklist. Participants will record such occurrences in the eDiary on the day of study intervention dosing and 6 subsequent days.

Severity grading of reactogenicity will occur automatically based on participant entry into the eDiary according to the grading scales presented Section 5.3, which are modified from the Toxicity Grading Scales for Healthy Adult and Adolescent Volunteers Enrolled in Preventive Vaccine Clinical Trials (DHHS 2007b). All solicited ARs (local and systemic) will be considered causally related to dosing.

If a participant reports a solicited AR with onset during the solicited period, but they did not record the event in the eDiary, then the event should be recorded by study staff in EDC.

If the event starts during the solicited period, but continues beyond 7 days after dosing, the participants should notify the site to provide an end date and close out the event in EDC, where reactogenicity is collected.

If the participant reported an event that started after the solicited period (ie, beyond 7 days after dosing), it should be recorded as an AE in EDC. Causality for these events will be determined per assessment by the Investigator.

Any solicited AR that meets any of the following criteria must be entered into the participant's source document and must also be recorded by the clinic staff in EDC, where reactogenicity is collected:

- Solicited local or systemic AR that results in a visit to a healthcare practitioner (medically attended AE).
- Solicited local or systemic AR lasting beyond 7 days poststudy intervention dosing.
- Solicited local or systemic AR that leads to participant discontinuation from study participation.
- Solicited local or systemic AR that otherwise meets the definition of an SAE.

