3.2. Objectives and Endpoints (Part B)

The objectives which will be evaluated in this study and endpoints associated with each objective are provided in Table 8.

Objectives	Endpoints
Primary	
• To evaluate the humoral immunogenicity (for noninferiority) of mRNA-1010 relative to that of a licensed SD seasonal influenza vaccine (Fluarix Quadrivalent) against 4 vaccine- matched influenza virus A and B strains at Day 29 in adults 18 to <65 years old.	 GMT at Day 29 as measured by HAI. Proportion of participants reaching seroconversion at Day 29 as measured by HAI.
• To evaluate the safety, including reactogenicity, of mRNA-1010.	 Frequency and severity of solicited local and systemic ARs during a 7-day follow-up period postinjection. Frequency and severity of any unsolicited AEs during the 28-day follow-up period postinjection. Frequency of any SAEs, MAAEs, AESIs, and AEs leading to discontinuation from Day 1 to Day 181/EoS.
Secondary	5
 To evaluate the humoral immunogenicity of mRNA-1010 (for superiority) relative to a licensed SD seasonal influenza vaccine (Fluarix Quadrivalent) against vaccine- matched influenza A and B strains at Day 29. 	 GMT at Day 29 as measured by HAI. Proportion of participants reaching seroconversion at Day 29 as measured by HAI.
• To further evaluate the humoral immunogenicity of each study arm against vaccine-matched influenza A and B strains at Day 29.	 The proportion of participants with HAI titer ≥1:40 at Day 29. GMFR comparing Day 29 to Day 1 (Baseline) as measured by HAI.
Exploratory (May be Performed)	
• To evaluate the humoral immunogenicity of mRNA-1010 relative to that of a licensed SD seasonal influenza vaccine (Fluarix Quadrivalent) against vaccine-matched influenza virus A and B strains at Day 181/EoS in a subset of participants.	 GMT at Day 181 as measured by HAI. Proportion of participants reaching seroconversion at Day 181 as measured by HAI.

Table 8:Objectives and Endpoints (Part B)

Objectives	Endpoints
• To evaluate the humoral immunogenicity of mRNA-1010 relative to that of a licensed SD seasonal influenza vaccine (Fluarix Quadrivalent) against vaccine-matched or vaccine-mismatched A and B strains.	 GMT and GMFR of nAbs by assays such as MN assays or alternative methods against vaccine-matched/mismatched strains on Day 29 compared with Day 1 (Baseline). GMT and GMFR of anti-HA antibodies as measured by HAI against vaccine- mismatched strains on Day 29 compared with Day 1 (Baseline).

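### The SAP's tables for MAAEs and for AEs leading to discontinuation are limited to unsolicited events, so solicited reactions that lead to a medical visit or withdrawal are left out of two primary safety endpoints

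*SAP*

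**What the plan says.** **Endpoints.** Protocol Tables 2, 8 and 12 make MAAEs and AEs leading to discontinuation primary safety endpoints. The Part B wording is "Frequency of any SAEs, MAAEs, AESIs, and AEs leading to discontinuation from Day 1 to Day 181/EoS"; Part C matches it, and Part A lists the same items separately. Protocol 5.3.3 defines an MAAE as an AE that brings about an unscheduled visit to a practitioner, and sets no condition on whether the diary asked about it.

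**Solicited reactions.** SAP 2.5.5.1 states: "Solicited ARs are a subset of AEs consisting of selected signs and symptoms". Protocol 2.8.3.9 and SAP 2.5.5.1 list four situations that require site entry of a solicited reaction: a healthcare visit, persistence past 7 days, discontinuation, and seriousness. The first is tagged in the protocol as a medically attended AE and in the SAP as an MAAE. Any such reaction "must also be recorded by the clinic staff in EDC, where reactogenicity is collected". SAP 3.5.5.1 calls this form the Reactogenicity CRF.

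**Tables.** SAP 2.5.5.2 defines an unsolicited AE as one not solicited through the diary. The 28-day overview in SAP 2.5.5.2.1 has the rows "Any unsolicited medically attended TEAEs" and "Any unsolicited TEAEs leading to discontinuation from participation in the study", and SAP 2.5.5.2.2 repeats them by SOC and PT. For the full follow-up, SAP 2.5.5.2.2 plans "Summary tables for all unsolicited SAEs, AESIs, MAAEs, AE leading to discontinuation from the study, and TEAE leading to death through Day 181/EoS". Parts B and C refer back to these sections.

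**The concern.** The endpoint covers any MAAE and any AE leading to discontinuation, while the tables that report it cover only the unsolicited part. The part left out is the reactogenicity-driven one, and Protocol 2.8.3.9 deems all solicited reactions causally related to dosing. If one vaccine is more reactogenic, the tables would understate both endpoints more in that arm. The arm comparison on a primary safety objective would then look more even than the endpoint as defined would show.

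**Working it through.** Neither document gives a rate of medically attended or withdrawal-causing solicited reactions, so there is no planned figure to reproduce. The check follows one event from definition to table: a Grade 2 fever on Day 2, seen in urgent care. In a variant, the participant also withdraws because of it.

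1. *Is it an AE?* Yes. Fever is on the diary list, and solicited reactions are a subset of AEs (SAP 2.5.5.1).
2. *Is it an MAAE?* Yes. Protocol 5.3.3 gives urgent care as an example of a qualifying visit, and Protocol 2.8.3.9 and SAP 2.5.5.1 tag such a reaction as medically attended.
3. *Where is it recorded?* In EDC with the reactogenicity data. A reaction that starts in the window stays there even if it lasts beyond 7 days; only one starting later becomes an ordinary AE (Protocol 2.8.3.9).
4. *Is it unsolicited under SAP 2.5.5.2?* No. The diary asked for it.
5. *Is it in the 28-day MAAE or discontinuation rows?* No. Each row carries the word unsolicited (SAP 2.5.5.2.1 and 2.5.5.2.2).
6. *Is it in the Day 181 tables?* On the natural reading, no. The word heads the list that contains both endpoints.
7. *Is it identified in the solicited-reaction tables?* Only as a Grade 2 fever. SAP 2.5.5.1 plans overall rates, grade, day of onset, duration, continuation past 7 days and possibly delayed onset. Nothing is split by medical attendance or withdrawal.
8. *Does it appear elsewhere?* The withdrawal does. Protocol 2.7.1.1 has its own reason code, "Withdrawal due to solicited AR/reactogenicity", separate from the adverse-event reason, and SAP 2.5.2.1 tabulates reasons by vaccination group. The urgent-care visit appears in no planned table as a medically attended event.

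*Contrast with serious events.* The 28-day rows for serious TEAEs in the same lists do not carry the word. A solicited reaction starts within 7 days, so a serious one falls inside that 28-day period, and SAP 2.5.1 also assigns SAEs to the 7-day analysis period. Only the Day 181 description is out of line for SAEs.

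*Effect on the comparison.* For either endpoint, let q1 and q0 be the proportions of the mRNA-1010 and comparator arms whose only qualifying event is a solicited reaction. Then:

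tabulated arm difference = difference on the endpoint as defined − (q1 − q0).

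If q1 = q0, the difference is unchanged and only the two rates are too low. If q1 > q0, the excess in the mRNA-1010 arm is understated by q1 − q0.

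*Scale, with q assumed at 0.1% to 1% per arm:*

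- Parts B and C: 1500 × 0.001 = 1.5 and 1500 × 0.01 = 15 participants per arm.
- Part A: 1200 × 0.001 = 1.2 and 1200 × 0.01 = 12 participants per arm.

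**The case against.** The best counter-argument is that the SAP is inconsistent, not restrictive. In SAP 2.5.5.2 one sentence speaks of unsolicited TEAEs over 28 days, and the next promises MAAEs and AEs leading to discontinuation throughout the study without that qualifier. The MAAE listing in SAP 2.5.5.2.1 is also unqualified. Protocol 2.9.5.2 plans MAAE and discontinuation counts with no such limit. In the Day 181 sentence, the adjective could be read as attaching to SAEs alone. The tension is real. But the unqualified sentence and the listing both sit in the section on unsolicited events, and neither specifies a table that brings solicited reactions in. The 28-day rows carry the word one by one, while the serious-event rows beside them do not, so it looks deliberate. The protocol text cannot settle the matter, because SAP 1 gives the SAP precedence where methods differ, and SAP 5 declares no change.

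A second argument is that safety is assessed by clinical review, and that solicited reactions are tabulated by arm and grade, so a reactogenicity difference would be visible. That is correct as far as it goes. Those tables show how severe reactions were; the two endpoints ask whether an event led to care or withdrawal.

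A third argument is that neither document says these reactions are kept off the AE form, and the eCRF and its completion guidelines are not available. This stands as a caveat. A duplicate AE-form entry would still not be unsolicited under the SAP's own definition, so whether it was counted would depend on the programmer.

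**Conclusion.** For MAAEs and AEs leading to discontinuation, the SAP's endpoint tables are narrower than the protocol's primary safety endpoints, and the narrowing is not declared. The size is unknown: 1.5 to 15 participants per 1500-person arm rests wholly on the assumed 0.1% to 1%. It also takes those participants to have no qualifying unsolicited event, since anyone who does is already counted.

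Three stronger readings are tempting, and the documents do not support them.

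- *A reader might infer that these events disappear from all outputs.* Reactogenicity withdrawals remain in disposition by reason. For seven of the eleven reactions in Protocol Table 16 (injection-site pain, axillary swelling or tenderness, headache, fatigue, myalgia, arthralgia, chills), an emergency room visit is Grade 4 by definition, and grades are tabulated. A lesser visit for a Grade 1 to 3 reaction is what goes unidentified.
- *A reader might infer that serious reactions are missed too.* The unqualified 28-day rows cover them.
- *A reader might infer a known bias in favour of mRNA-1010.* The omission is differential only if the rates of such reactions differ between arms, and the documents give no rates.

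**What to change.** In SAP 2.5.5.2.1 and 2.5.5.2.2, for all Parts:

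- Delete *unsolicited* from the medically attended and discontinuation rows and from the description of the Day 181 tables. The latter also brings the Day 181 SAE wording into line with the 28-day rows.
- Count MAAEs and AEs leading to discontinuation from unsolicited AEs plus the solicited reactions entered on the Reactogenicity CRF because they were medically attended or led to discontinuation. Include withdrawals coded to solicited reactions or reactogenicity in the discontinuation endpoint.
- Use the Safety Set as denominator. Solicited reactions are otherwise analysed on the Solicited Safety Set, so this needs stating.
- Show the solicited and unsolicited contributions as sub-rows.

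If the sponsor does want unsolicited events only, the minimum is to say so in the endpoint definitions and add a table of medically attended and discontinuation-causing solicited reactions by arm.

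The cost is SAP wording, some programming to combine two sources that sites must already record, and slightly higher reported rates. One check comes first: that the eCRF shows which criterion each Reactogenicity CRF entry met, since neither document describes such a field. Protocol 5.7.1 already reports the Part A primary immunogenicity results, so any revised Part A tables should be recorded as a change in SAP 5.
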